2 INTRODUCTION: BACKGROUND INFORMATION AND SCIENTIFIC RATIONALE

2.1 BACKGROUND INFORMATION

The proposed study is in the field of radiation oncology, where functional imaging will be used to assess the outcome of radiation therapy (RT) for liver cancer patients.

Radiation therapy for liver cancer

Liver cancer is a prevalent public health problem. The number of new liver cancer cases was estimated to be 39,000 in 2016. Furthermore, liver cancer was estimated to represent approximately 5% of all cancer deaths in 2016. The five-year survival rate of all liver cancers is estimated to be 18% [1]. Liver cancer is comprised of intrahepatic bile duct cancers (25%) and hepatic cell carcinomas (75%). Since less than 25% of hepatic cell carcinomas are eligible for surgical resection, radiation therapy is a treatment option for many liver cancer patients [2,3]. However, therapy success is suboptimal. Optimization of cancer therapy based on a patient's unique biological characteristics, called "personalized cancer therapy", is becoming achievable [4]. One aspect of the patient's unique tumor microenvironment is the characteristics of blood perfusion. Though there are several imaging modalities that can quantify perfusion, DCE-CT is one accessible option. In addition, this study focuses on using SBRT as the radiation therapy treatment modality. SBRT delivers radiation therapy over a short time interval (typically, 3-8 sessions). This differs from conventional external beam radiation therapy, where a typical treatment course can last anywhere from 10 to 30 sessions, or more (this is dependent on the total radiation dose to the tumor). Historical experiences using large-field liver RT have had limited success, because tolerable doses of whole-liver RT (approximately 30 Gy) are insufficient to control most lesions [5-7]. Higher doses of whole-liver RT are associated with a significant risk of radiation-induced liver damage. Recent data have demonstrated that high-dose partial liver RT and SBRT may be safer and more effective than whole-liver RT for patients with liver tumors [8-12].

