2.2 RATIONALE

We are proposing a pilot study to evaluate the feasibility of Dynamic Contrast Enhanced Computed Tomography (DCE-CT) imaging for outcome assessment of radiation therapy (RT) for the treatment of liver HCC and metastases. DCE-CT, also known as perfusion CT, is a functional imaging modality that uses repeated computed tomography imaging after injection of an iodine-based contrast agent. DCE-CT allows for a quantitative assessment of blood flow in malignant solid tumors and healthy surrounding tissue. This data provides for patient-specific information about the blood-flow characteristics of the tumor, as well as surrounding healthy tissue. The goal of this study is to use each patient's tumor perfusion information for outcome assessment of radiation therapy for the treatment of liver HCC and metastases.

In this study, we propose to focus on Stereotactic Body Radiation Therapy (SBRT) as the radiation therapy treatment modality. SBRT delivers radiation therapy over a short time interval (3-8 sessions). This differs from conventional external beam radiation therapy, where a typical treatment course can last anywhere from 10 to 30 sessions. The smaller number of treatment session associated with SBRT may have unique biological effect on the tumor vasculature not found in the conventional form of radiation therapy.

Measuring change in perfusion after therapy may be used to assess the success of therapy. Assessment of RT is traditionally accomplished using change in tumor morphology, using the RECIST criteria [16]. However, this tumor volume change does not necessarily describe change in tumor physiology. In addition, large necrotic regions of tissue may be included in the morphological quantification[18]. The utilization of DCE-CT for outcome assessment in RT has

been previously studied in several cancer sites, including the liver [1,3-5]. However, no study, to the best of our knowledge, has attempted to use DCE-CT as an outcome assessment tool for SBRT treatment of liver cancer. This study aims to determine if perfusion changes from SBRT of liver cancer may be used for outcome assessment and prediction of prognosis.

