3 OBJECTIVES AND PURPOSE

Primary Objective: Investigate the association between the delivered radiation therapy dose distribution and the change in perfusion measurement following treatment.

The goal of this study is to determine if perfusion, as measured from DCE-CT, can be imaged in the liver to assess treatment response from radiation therapy. Total therapeutic radiation dose delivered during SBRT will be used as a surrogate measurement for treatment response. This may provide unique physiological information that will improve outcome assessment, as well as predict treatment efficacy, for patients treated with SBRT for liver cancer.

Specifically, this study investigates if perfusion characteristics, as well as their respective changes from pre-treatment to post-treatment DCE-CT imaging, may have a relationship with therapeutic radiation dose. This will potentially provide a strong measure of treatment prognosis that will

provide the physician with crucial information that may guide follow-up treatments if prognosis is predicted to be poor. Additionally, we will be able to assess if DCE-CT imaging parameters changes after liver SBRT treatment are reproducible and relative to normal liver function.

Secondary Objective: Explore any demographic differences in perfusion metrics.

The secondary objective will be used to provide descriptive information on demographic differences in perfusion metrics. Should a larger study be warranted this information will be crucial in study design and analysis to control for demographic differences.

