4 STUDY DESIGN AND ENDPOINTS

4.1 DESCRIPTION OF THE STUDY DESIGN

This is a pilot study designed to evaluate the feasibility of DCE-CT imaging for outcome assessment of radiation therapy for the treatment of liver cancer. Because this is a pilot study, no clinical decisions or interventions will deviate from standard of care.

Pre-treatment perfusion assessment will be performed before the start of SBRT. The first Post-treatment perfusion assessment will be within six hours after the end of the first fraction of SBRT. The final Post-treatment perfusion assessment will be six weeks after the end of SBRT (with an allowed time window of 4-8 weeks).

Step 1 (Enrollment & Screening):

Patients with liver cancer receiving stereotactic body radiation (SBRT) as part of their standard of care will be eligible for study enrollment. SBRT is similar to conventional, photon-based radiation therapy. SBRT differs from conventional radiation therapy by utilizing less treatment sessions, also call ‘a fraction’, and a higher radiation dose per treatment session. Typically, SBRT is 5 fractions, whereas conventional radiation therapy may have 10 to 30 fractions, depending on the total prescribed radiation dose. DCE-CT imaging will be added at three specific time points of the clinical workflow for the quantification of perfusion.

Step 2 (Pre-treatment perfusion assessment):

Subjects will have DCE-CT imaging before the initiation of radiation therapy. Under SOC, all patients receiving radiation therapy undergo a planning CT simulation session. This session of CT imaging produces the CT study that will be used to create the radiation treatment plan. Under this

study, an additional DCE-CT scan will be acquired to quantify a patient's baseline perfusion characteristics.

Step 3 (Initiation of Radiation Therapy and Post-treatment perfusion assessment):

Subjects will begin radiation therapy for treatment of liver cancer or metastases. Each individual treatment session, also known as a "fraction", will utilize on-board imaging to ensure localization of treatment to the patient's unique anatomy for each session. This is the SOC with no modifications to the radiation treatment characteristics. Subjects will have DCE-CT imaging within six hours of receiving the first fraction of radiation therapy to assess the SBRT related changes to baseline perfusion characteristics.

Step 4 (Completion of Radiation Therapy):

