4.2 STUDY ENDPOINTS

4.2.1 PRIMARY ENDPOINTS

Primary endpoints include total therapeutic radiation dose delivered and DCE-CT profusion metrics at baseline, following first treatment, and 6 weeks after treatment. Profusion metrics include: KTrans (aka extraction-flow product), blood volume, and blood flow.

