5 STUDY ENROLLMENT AND WITHDRAWAL

5.1 PARTICIPANT INCLUSION CRITERIA

In order to be eligible to participate in this study, an individual must meet all of the following criteria:

1. Provision to sign and date the consent form
2. Stated willingness to comply with all study procedures and be available for the duration of the study
3. Be a Male or Female aged 18-100
4. Diagnosed with Liver HCC or metastases
5. Must be receiving or will plan to receive SBRT for Liver HCC or metastases

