10.4.2 ANALYSIS OF THE PRIMARY EFFICACY ENDPOINT(S)

The primary endpoint of this study is change in profusion metrics from baseline to end of first radiation treatment and 6-weeks after treatment has ended. Additionally, total radiation dose delivered from SBRT will be captured and used as a surrogate measurement for treatment response.

Individual profusion metrics will be plotted as well as means with corresponding standard errors for the three time points. Change in profusion metrics from baseline versus radiation dose received will be plotted separately for the two follow-up DCE-CT scans. Correlation between change in profusion and total radiation dose received will be evaluated using Spearman's correlation coefficient.

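### The primary correlation uses total dose at both follow-up scans although the number of fractions is not fixed; if schedules vary, this can misrank exposure and usually dilutes the dose-perfusion association

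*Combined protocol and SAP*

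**What the plan says.** Section 4.2.1 defines the dose variable: "Primary endpoints include total therapeutic radiation dose delivered". Section 3 gives its role: "Total therapeutic radiation dose delivered during SBRT will be used as a surrogate measurement for treatment response". Section 10.4.2 plots perfusion change against dose separately for the two follow-up scans and then states: "Correlation between change in profusion and total radiation dose received will be evaluated using Spearman's correlation coefficient". Section 10.1 likewise compares perfusion change with delivered dose and defines it no further.

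On fractionation, section 2.1 says "SBRT delivers radiation therapy over a short time interval (typically, 3-8 sessions" and section 2.2 repeats the range. Section 4.1 is narrower: "Typically, SBRT is 5 fractions, whereas conventional radiation therapy may have 10 to 30 fractions". The only related inclusion criterion (5.1) is "Must be receiving or will plan to receive SBRT for Liver HCC or metastases", and radiation treatment follows standard of care unmodified (4.1). Dose per fraction, number of fractions and any fractionation-adjusted dose appear nowhere as an exposure, covariate, stratum or sensitivity analysis. The eCRF list in section 11 does not name fraction number.

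Sections 4.1, 7.1 and 7.2.3 place the first follow-up scan within six hours of the first fraction. Section 10.2 states that the primary analysis involves no formal hypothesis test.

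**The concern.** Spearman's coefficient uses only ranks, so all that the dose variable contributes is the order in which it places patients. Total dose orders them by gray alone. Two courses with the same total in 3 and in 8 fractions are tied, although their dose per fraction differs by a factor of 8/3. Under the usual linear-quadratic account they are not equal exposures.

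The first scan raises a simpler problem. When it is taken, most of the course has not been delivered, yet the plan relates it to the whole-course total.

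Dose is also the stand-in for treatment response, and section 2.1 says the data will be used to power a larger study. If exposure is misranked, the estimate carried into that study will tend to be too small, and 10 to 15 patients give little chance of noticing.

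**Working it through.** **Inputs from the documents.** Fractions 3-8 (2.1, 2.2), typically 5 (4.1). Sample size 10 to 15 (10.5), where 50 x 0.40 x (1 - 0.25) = 15 reproduces the stated maximum. The plan states no target correlation, power or alpha, so there is no further figure to reproduce. The dose cut-points 36 and 54 Gy come from the dose-control study cited in 2.1.

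**Assumptions.** The documents give no alpha/beta; 10 Gy is used, with 3 and 20 Gy as a range. Total dose D is uniform over 36-60 or 45-60 Gy. Each course has n equal fractions. The courses below are arithmetic illustrations, not proposals for treatment.

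**Step 1: first scan, no model.** Dose given by the scan = D/n.
- 45 Gy in 3: 45/3 = 15 Gy given.
- 54 Gy in 8: 54/8 = 6.75 Gy given.

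Total dose ranks the second course higher; at the time of the scan it has delivered less than half as much.

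**Step 2: whole course.** BED = D x (1 + (D/n)/(alpha/beta)).
- 54 Gy at alpha/beta 10: in 3 fractions, 54 x (1 + 18/10) = 151.2; in 5, 54 x (1 + 10.8/10) = 112.3; in 8, 54 x (1 + 6.75/10) = 90.5. The spread is 151.2/90.5 = 1.67-fold at one total dose.
- 45 Gy in 3 at alpha/beta 10: 45 x (1 + 15/10) = 112.5, above the 90.5 for 54 Gy in 8. The inversion also holds at alpha/beta 3 (270 against 175.5) and 20 (78.8 against 72.2).

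**Step 3: rank agreement in a sample of 10.** Mean Spearman correlation of total dose with BED (alpha/beta 10) by simulation. In the 70% and 90% rows the remaining patients are split equally between 3 and 8 fractions.

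| Schedule mix | 36-60 Gy | 45-60 Gy |
|---|---|---|
| 3, 5, 8 equally likely | 0.69 | 0.48 |
| 70% have 5 fractions | 0.83 | 0.67 |
| 90% have 5 fractions | 0.94 | 0.87 |
| one number for all | 1 | 1 |

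In the first row, total dose and BED are negatively correlated in about 0.4% of samples (36-60 Gy) and about 6% (45-60 Gy).

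**Step 4: effect on the correlation of interest.** Suppose the true Spearman correlation of perfusion change with BED is 0.60 (assumed), with totals of 36-60 Gy in the first three cases. The large-sample correlation with total dose at alpha/beta 10 (range over 3 to 20) is:
- all courses 5 fractions: 0.60;
- 70% at 5 fractions: 0.51 (0.47-0.54);
- 3 to 8 fractions, unrelated to total dose: 0.49 (0.43-0.53);
- total dose rising with fraction number: 0.28 (-0.06 to 0.50);
- total dose falling as fraction number rises: 0.59.

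The chance that a sample of 10 shows the wrong sign is 3% with all courses at 5 fractions, 5% with 70% at 5, 8% with fractions unrelated to dose, and 22% if total dose rises with fraction number. With BED it is 3-4% throughout.

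**The case against.** **Most courses may be 5 fractions.** Section 4.1 calls 5 typical, and the 3-8 range describes SBRT in general; it is not a rule of this trial. This stands. It is why the size must be shown across schedule mixes, and why the loss may be small or nil.

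**Total dose was chosen on a stated basis.** The dose-control evidence in 2.1 is reported by nominal dose, so total dose follows its own source, while BED needs an alpha/beta that the documents do not supply. This supports keeping total dose in the report. That evidence concerns local control, however, and does not show that equal totals in different numbers of fractions are equal exposures for perfusion.

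**The analysis is descriptive.** This is true (10.2), and no test decision is at risk. A reader might infer an outright error in the primary analysis; that is too strong. What is at risk is an attenuated exploratory estimate.

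**The protocol's own rationale.** Section 2.2 says "The smaller number of treatment session associated with SBRT may have unique biological effect on the tumor vasculature", and a reader might take this as the protocol stating that 3 and 8 fractions act differently on vessels. It does not: the sentence goes on to contrast SBRT with conventional radiation therapy, and it says only that there may be an effect. The case for adjusting within SBRT rests on the dose actually given by the first scan and on the linear-quadratic assumption.

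**Conclusion.** The point holds as a cheap improvement. The plan relates both follow-up scans to total dose, does not fix fraction number and makes no adjustment for it. If schedules vary, the expected result is dilution: an assumed correlation of 0.60 becomes about 0.5 under a mix unrelated to dose. If every course has the same number of fractions, nothing is lost.

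A reader might infer that the association would be reversed. The documents do not support that as an expectation. Systematic reversal, or attenuation close to zero, needs total dose to rise with fraction number, and no section describes such a pattern; otherwise a wrong sign arises mainly by chance at this sample size.

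The 6-week figures depend on the assumed alpha/beta, dose range and schedule mix. The first-scan point depends only on fraction number varying and on the scan following a single fraction.

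**What to change.** In 4.2.1 and 10.4.2:
- Record number of fractions and dose per fraction from the treatment record.
- For the first-scan correlation and plot, use dose delivered by the time of the scan. This definition also copes with the wider mid-treatment window in the schedule of events (7.2.7).
- For the 6-week correlation and plot, use BED computed from delivered dose and fractions, with alpha/beta = 10 Gy and repeated at 3 Gy. Report it alongside the total-dose correlation, with points marked by fraction number.

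The cost is some plan wording, two recorded items and simple derived variables, with no extra patients or scans. The downside is that an alpha/beta must be assumed, but ranks change little: mean Spearman agreement between BED at 10 and at 3 Gy is about 0.97-0.98 in the simulation with 3, 5 and 8 fractions equally likely. If all courses turn out to have one schedule, the BED and total-dose rankings coincide. The change affects the analysis only, not treatment.

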10.4.3 ANALYSIS OF THE SECONDARY ENDPOINT(S)

To assess descriptively whether there are signs that profusion metrics differ based on patient demographics the following demographic information will be captured; age, sex, race, clinical stage at diagnosis. Change in profusion metrics from baseline to each of the two follow-up DCE-CT scans will be stratified by demographic information and descriptive statistics will be presented, e.g., sample size, mean, median, standard deviation, and range.

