Primary endpoints include therapeutic radiation dose delivered and DCE-CT profusion metrics at baseline, following first treatment, and 6 weeks after treatment. Profusion metrics include: KTrans (aka extraction-flow product), blood volume and blood flow.
 - ***Secondary Endpoint:***
Demographic information (e.g., sex, age, race, etc.) will be combined with primary profusion endpoints.
- Population:**
- ***Sample size***
 - *Maximum number of participants that can be enrolled is 15 (allow for screen failures)*
 - *Minimum number of participants to be enrolled 10 (number of participants needed to answer scientific question/aims)*
 - ***Gender*** Male and Female
 - ***Age Range*** 18-100
 - ***Demographic group*** We expect patients enrolled on the study to have consistent gender, age, racial, and ethnic distributions to the population living in the state of Colorado.
 - ***General health status*** Liver HCC or Metastases.
 - ***Geographic location*** Receiving treatment at UC Metro

Phase: *Pilot*

**Number of
Participating Sites
enrolling
participants:** *1*

Study Duration: *12 months*

SCHEMATIC OF STUDY DESIGN

[figure not shown]

TABLE OF CONTENTS

STATEMENT OF COMPLIANCE	2
LIST OF ABBREVIATIONS	3
PROTOCOL SUMMARY / SYNOPSIS	4
SCHEMATIC OF STUDY DESIGN	5
1 PARTICIPATING SITES	8
2 INTRODUCTION: BACKGROUND INFORMATION AND SCIENTIFIC RATIONALE	8
2.1 Background Information	8
2.2 Rationale	11
2.3 Potential Risks and Benefits	12
2.3.1 Known Potential Risks	12
2.3.2 Known Potential Benefits	13
3 OBJECTIVES AND PURPOSE	13
4 STUDY DESIGN AND ENDPOINTS	14
4.1 Description of the Study Design	14
4.2 Study Endpoints	15
4.2.1 Primary Endpoints	15
4.2.2 Secondary Endpoint	15
5 STUDY ENROLLMENT AND WITHDRAWAL	16
5.1 Participant Inclusion Criteria	16
5.2 Participant Exclusion Criteria	16
5.3 Strategies for Recruitment and Retention	16
5.4 Participant Withdrawal or Termination	16
5.4.1 Reasons for Withdrawal or Termination	16
5.4.2 Handling of Participant Withdrawals or Termination	17
5.5 Premature Termination or Suspension of Study (Study Stopping Rules)	17
6 STUDY AGENT	17
6.1 Study Agent(s) and Control Description	17
7 STUDY PROCEDURES AND SCHEDULE	18
7.1 Study Procedures/Evaluations	18
7.2 Study Schedule	19
7.2.1 Screening	19
7.2.2 Enrollment/Baseline	19
7.2.3 Follow-up	19
7.2.4 Final Study Visit	19
7.2.5 Early Termination Visit	20
7.2.6 Unscheduled Visit	20
7.2.7 Schedule of Events Table	20
7.4 Prohibited Medications, Treatments, and Procedures	21

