10.5 SAMPLE SIZE

The study will enroll a minimum of 10 patients with a maximum enrollment of 15 patients to allow for screen failures and dropouts. This sample size was based the number of patients that would be reasonable for the Department of Radiation Oncology to recruit within a year. The Department of Radiation Oncology treats approximately 50 liver cancer patients with SBRT per year. Assuming an enrollment rate of 40% and a dropout rate of 25%, a conservative estimate is enrolling a maximum of 15 patients in 12 months.

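### Section 10.4.3 stratifies by age with no cut-points; plotting change against age with Spearman's coefficient, as already planned for dose, would lose nothing to grouping

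*Combined protocol and SAP*

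**What the plan says.** Section 10.4.3 names the variables: "the following demographic information will be captured; age, sex, race, clinical stage at diagnosis". Change in each perfusion metric, from baseline to each of the two follow-up scans, then "will be stratified by demographic information and descriptive statistics will be presented, e.g., sample size, mean, median, standard deviation, and range". No other method is given for the secondary objective. The section states no age cut-point, no number of groups for age, race or stage, and no continuous analysis of age.

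The eligible age range is wide (section 5.1: "Be a Male or Female aged 18-100") and the sample is small (section 10.5: "The study will enroll a minimum of 10 patients with a maximum enrollment of 15 patients"). Section 3 describes the secondary objective as descriptive but gives it a purpose: "Should a larger study be warranted this information will be crucial in study design and analysis to control for demographic differences".

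Section 10.4.2 treats dose, the other continuous covariate, differently. It plots change against dose separately for the two follow-up scans and evaluates the correlation with Spearman's coefficient.

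**The concern.** A continuous variable can be stratified only after it is cut. With no cut fixed in advance, the analyst can choose one after seeing which division shows a difference, and in a sample this small moving one or two patients across a boundary can change the picture. Even an honest cut throws away the ordering of ages within each group.

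What is at stake is the quality of a descriptive answer. The plan wants to know whether age should be allowed for in a larger study. The data to be collected can answer that somewhat better than the stated method will, using a tool the plan already applies to dose.

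**Working it through.** **Inputs from the documents.** Enrollment of 10 to 15 and the recruitment assumptions (section 10.5); age range 18 to 100 (section 5.1); stratifying variables (section 10.4.3). **Assumed, because the documents do not say:** the shape of the age distribution, the number and position of cuts, a linear age trend, and the share of patients in any one category.

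**1. The plan's own figure.** 50 patients per year × 0.40 enrolled = 20; 20 × (1 − 0.25) = 15, which matches the maximum in section 10.5. Section 5.3 gives 10 from the same inputs. That does not follow arithmetically, though it may be a cautious target. I use 10 and 15 as the range. If the 25% dropout acts after enrollment, 10 × 0.75 = 7.5 and 15 × 0.75 = 11.25 would remain.

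**2. Information lost by grouping age.** For a linear trend, the share kept is the share of age variance that lies between groups. With k equal-sized groups:
- Uniform age: kept = 1 − 1/k².
- Normal age: kept = (1/k) Σ mⱼ², where mⱼ is the mean standardised age in group j. For k = 2, m = ±2φ(0) = ±0.798, so kept = 0.798² = 2/π = 0.637 and lost = 0.363.

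| Equal groups | Lost, normal age | Lost, uniform age | Average per group at N = 7.5, 10, 15 |
|---|---|---|---|
| 2 | 36% | 25% | 3.8, 5.0, 7.5 |
| 3 | 21% | 11% | 2.5, 3.3, 5.0 |
| 4 | 14% | 6% | 1.9, 2.5, 3.8 |
| 5 | 10% | 4% | 1.5, 2.0, 3.0 |

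A two-way cut away from the median loses more. With normal age the share kept is φ(c)²/[p(1 − p)], where p is the proportion below the cut c. The loss is 38% at a 40/60 split and 42% at 30/70. Keeping age continuous loses nothing to grouping in any row.

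**3. What the loss means in practice.** In simulation with 12 patients and a true correlation of 0.5 (both assumed), the estimated association has the wrong sign in about 5% of studies with Spearman on age and about 8% with a median split. The gain is real but small.

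**4. Small race and stage groups.** The 95% interval for an SD, as a multiple of the estimate, is √[(n − 1)/χ²] at the 97.5% and 2.5% points of χ² with n − 1 degrees of freedom:
- n = 1: no SD exists.
- n = 2: 0.45 to 31.9.
- n = 3: √(2/7.38) = 0.52 to √(2/0.0506) = 6.3.
- n = 10: 0.69 to 1.83.
- n = 15: 0.73 to 1.58.

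A category holding an assumed 15% of patients has one or two members with probability 0.62, 0.59 and 0.52 at n = 10, 12 and 15.

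**The case against.** The strongest reply is that this is a descriptive pilot. Section 10.4.3 looks only for signs of difference, and the listed statistics are examples, so no SD is required where a group has one patient. Sample size and range are listed beside the SD, so a reader would see how few patients lie behind it. Spearman's coefficient is also imprecise here. An observed 0.45 in 12 patients (illustrative) has an approximate 95% interval of −0.20 to 0.83, from Fisher's transformation with variance (1 + r²/2)/(n − 3). Three metrics at two scans would add six such coefficients. All of this stands. It keeps the severity low, but it gives no reason to cut age when dose is left continuous.

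A reader might draw four stronger conclusions. The documents support none of them.
- *A fixed third of the age information is lost.* That needs a two-way split near the median, roughly normal age and a linear trend. The documents specify none of these.
- *Strata will generally hold one to three patients.* A median split of age leaves about 5 to 7 per group at 10 to 15 patients. For sex, with an assumed even mix, the smaller group has three or fewer with probability 34% at 10 patients and 3.5% at 15, and the larger group always exceeds three. Very small groups are plausible mainly for race, stage or fine age bands.
- *Splitting shrinks the association itself.* A correlation with a median-split variable is multiplied by about √(2/π) = 0.80 by construction, so a drop in the coefficient is mostly a change of scale.
- *Stratum SDs will be the planning values for the next study.* No section says so. Section 3 speaks of controlling for demographic differences, section 2.1 says the study's data as a whole will be used to power a larger study, and section 10.4.1 promises descriptive statistics for every measured variable, which implies a whole-sample SD.

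**Conclusion.** The point holds as a free improvement of low severity. Section 10.4.3 requires age to be grouped, fixes no grouping, and so leaves the cut open to choice after the data are seen. Assuming a linear trend, the loss of information on age is 36% for a median split with roughly normal age, 25% with uniform age, and 21% or less with three or more equal groups. The true figure cannot be stated because the documents do not give the grouping or the age distribution.

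The small-stratum issue is secondary. Some race and stage groups may hold one to three patients, where an SD is undefined or nearly uninformative. The plan's flexible list and the displayed sample sizes largely contain the risk of misreading. Nothing here affects the primary analysis, and the change would not make demographic estimates from 10 to 15 patients precise.

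**What to change.** In section 10.4.3, take age out of the list of stratifying variables and state that it is kept continuous: change in each perfusion metric is plotted against age, separately for each of the two follow-up scans, with Spearman's coefficient and the number of patients reported descriptively. This mirrors section 10.4.2. If summaries by age group are also wanted, state the cut-points before the data are examined.

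As an option, show individual values by sex, race and stage, so that groups of one to three patients are read as single observations and not through a mean and SD.

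The cost is one or two sentences and a few plots. It needs no new data and no extra patients.
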